### **11.2.4 Treatment of Adverse Events**

Adverse events that occur during the study will be treated, as necessary, by established standards of care. If such treatment constitutes a deviation from the protocol, the subject should be withdrawn from the study and the reason and date of withdrawal must be documented in the eCRF. The decision about whether the subject may continue in the study will be made by the sponsor after consultation with the investigator and/or Medical Monitor.

If a subject experiences an intolerable AE , the investigator must decide whether to withdraw the subject from the study and/or treat the subject. Special procedures may be recommended for the specific study drug, such as the collection of a serum sample for determining blood concentrations of study drug, or treatment regimens, as appropriate.

It is **NOT** necessary to unblind a subject’s treatment assignment in most circumstances, even if an SAE has occurred. If unblinding is necessary, see [Section 9.5](#) for a description of the unblinding procedures.

### **11.2.5 Follow-up**

All ongoing SAEs at the time of discontinuation will be followed (up to a maximum of 30 days after the last dose of study drug) to a satisfactory resolution, or until it becomes stable, or until it can be explained by another known causes (i.e., concurrent condition or medication) and clinical judgment indicates that further evaluation is not warranted. All ongoing AEs at the time of discontinuation will be followed for up to 7 days. All findings relevant to the final outcome of an AE must be reported in the subject’s medical record and recorded on the eCRF page.

## 11.2.6 Reporting of Adverse Events

### 11.2.6.1 Serious Adverse Events

The investigator or designee must report all SAEs promptly to Noven Pharmacovigilance within 24 hours of first becoming aware of the event by completing, signing and dating the SAE Form (within the eCRF), verifying the accuracy of the information recorded in the form with the source documents.

**All SAEs, irrespective of relationship to study treatment, must be reported to Noven as soon as possible but no later than 24 hours using the appropriate SAE form within the eCRF.**

It is very important that the SAE form (within the eCRF) be filled out as completely as possible at the time of the initial report. This includes the investigator's assessment of causality. All SAEs must be followed to resolution, or if resolution is unlikely, to stabilization. Any follow-up information received on SAEs should be forwarded within 24 hours of its receipt. If the follow-up information changes the investigator's assessment of causality, this should also be noted on the follow-up SAE form (within the eCRF). If eCRF system is down or not accessible for the site, the "Noven Serious Adverse Event Reporting Form (Noven SAE form)" must be used for reporting to Noven Pharmacovigilance. The site should use the eCRF system as the primary means to notify of the SAE (initial or follow-up). The Noven SAE "paper" form should only be used as the back-up option for notification if the eCRF system is down.

If the situation where the Noven SAE "paper" form is to be used, **all SAEs, irrespective of relationship to study treatment, must be reported to Noven as soon as possible but no later than 24 hours to:**

Email: [REDACTED]

SAEs, regardless of causality assessment, must be collected through the Termination Visit and for 30 days following study drug discontinuation, whichever is longer.

Any SAE judged by the investigator to be related to the study treatment should be reported to the sponsor regardless of the length of time that has passed since study completion.

The written report should be submitted on the SAE form (within the eCRF) provided for this purpose. At the time of first notification, the investigator or designee should provide the following information, if available:

- Protocol number
- Reporter (study site and investigator)
- Subject's study number
- Subject's age
- Subject's gender
- Date of first dose of study drug
- Date of last dose of study drug, if applicable
- Adverse event term
- The seriousness criteria that were met
- Date of occurrence of the event
- A brief description of the event and outcome to date
- Any actions taken in response to the SAE
- Concomitant medication at onset of the event
- Relevant medical history information
- Relevant laboratory test findings
- Investigator's opinion of the relationship to study drug ("Is there a reasonable possibility that the study drug caused the SAE?")
- Whether and when the investigator was unblinded as to the subject's treatment assignment

Preliminary SAE reports and/or any missing or additional relevant information concerning the SAE should be provided to the recipients of the initial information as soon as possible on a follow-up SAE form (within the eCRF), together with the following information (AE, date of occurrence, subject number, study ID, study drug, and site number) including copies of hospital case reports, autopsy reports and other documents requested by the sponsor; this will allow the follow-up information to be linked to the initial SAE report.

The investigator is required to comply with applicable regulations (including local laws and guidance) regarding the notification of his/her health authorities, institutional review board (IRB), principal and coordinating investigators, study investigators, and institutions.

#### **11.2.6.2 Nonserious Adverse Events**

All non-serious AEs will be reported to the Sponsor on an ongoing basis and will be captured in the eCRF.

### **11.2.7 Pregnancy Reporting**

All females of childbearing potential who participate in the study should be counseled on the need to practice adequate birth control and on the importance of avoiding pregnancy during study participation. Females should be instructed to contact the investigator or study staff immediately if pregnancy occurs or is suspected.

Male study participants will be instructed to practice birth control measures to prevent a partner's pregnancy during the subject's study participation and for 90 days following the last dose administration.

Pregnancy testing will be conducted prior to administration of study drug on every female of childbearing potential. A female who is found to be pregnant at the Screening Visit will be excluded from the study and considered to be a screening failure.

A female who becomes pregnant during study drug treatment will be immediately withdrawn from the study. Any female who becomes pregnant during treatment and within 30 days of discontinuing study drug will be followed by the investigator until birth or termination of pregnancy. Any pregnancy for which the estimated date of conception occurred prior to the Termination Visit of the study and for 30 days following study drug discontinuation, whichever is longer, must be reported.

If an adverse outcome of a pregnancy is suspected to be related to study drug exposure, this should be reported regardless of the length of time that has passed since the exposure to study treatment.

An induced abortion or a spontaneous abortion is considered to be a SAE and should be reported in the same timeframe and in the same manner as all other SAEs (see [Section 11.2.6.1](#)).

The investigator must report the pregnancy to Noven using the **Noven Pregnancy Notification Report form** via the same email address as for SAE reporting. The investigator should contact the designated individuals who receive SAE notification and record information related to the pregnancy on a **Noven Pregnancy Notification Report form** provided by the sponsor or its designee.

**Pregnancies must be reported to Noven as soon as possible, but no later than 24 hours to:**

Email: [REDACTED]

ET Visit assessments are required as soon as possible after learning of the pregnancy. The Clinical Site should record and maintain all relevant information on the appropriate study form and eCRF, including the follow-up and outcome of the pregnancy.

The outcome of all pregnancies (spontaneous miscarriage, elective termination, ectopic pregnancy, normal birth or congenital abnormality) should be followed-up and documented even if the subject was discontinued from the study (with the subject's consent). The Clinical Site must report all pregnancy follow-up information to the Sponsor using the Noven Pregnancy Follow-up Report form via email to [REDACTED] within 24 hours of receiving the pregnancy follow-up information. Congenital abnormalities/birth defects and spontaneous miscarriages should be reported and handled as SAEs. The Clinical Site must report all congenital abnormalities/birth defects and spontaneous miscarriages using the SAE form (within the eCRF) via email to [REDACTED] within 24 hours of receiving the information. Elective abortions without complications should not be handled as AEs.

## **12. DATA SAFETY MONITORING BOARD**

There will be no Data Safety Monitoring Board for this study.

## 13. STATISTICAL METHODS

### 13.1. Study Endpoints

#### 13.1.1 Primary Efficacy Endpoint

- WOMAC LK3.1 OA (pain) change from Baseline at Week 12

#### 13.1.2 Key Secondary Efficacy endpoints

- WOMAC LK3.1 OA (physical function) change from Baseline at Week 12
- WOMAC LK3.1 OA (stiffness) change from Baseline at Week 12

#### 13.1.3 Secondary Efficacy Endpoints

- WOMAC LK3.1 OA (pain) change from Baseline at Weeks 1, 2, 4, and 8
- WOMAC LK3.1 OA (physical function) change from Baseline at Weeks 1, 2, 4, and 8
- WOMAC LK3.1 OA (stiffness) change from Baseline at Weeks 1, 2, 4, and 8
- WOMAC LK3.1 OA (composite score) change from Baseline at Weeks 1, 2, 4, 8, and 12
- Change from Baseline in pain intensity assessed on an 11-point NRS at Weeks 1, 2, 4, 8, and 12
- Change from Baseline in pain intensity assessed on an 11-point NRS of a weekly average of all available daily pain scores at each week from Week 1 through 12
- Change from Baseline in Patient Global Assessment at Weeks 1, 2, 4, 8, and 12
- Patient Global Impression of Change (PGIC) at Weeks 1, 2, 4, 8, and 12
- Treatment Response: Reduction in the WOMAC LK3.1 OA Index (pain) of 2:30%, 2:50%, 2:70% and 2:90% at Weeks 1, 2, 4, 8, and 12
- Treatment Response: Reduction in the WOMAC LK3.1 OA Index (physical function) of 2:30%, 2:50%, 2:70% and 2:90% at Weeks 1, 2, 4, 8, and 12
- Treatment Response: Reduction in the WOMAC LK3.1 OA Index (stiffness) of 2:30%, 2:50%, 2:70% and 2:90% at Weeks 1, 2, 4, 8, and 12
- Proportion of subjects, the number of days, and the total number of rescue medication tablets used during the treatment phase
- The onset of the effect: Pain intensity assessed on an 11-point NRS change from Baseline
- Mini-OA Knee and Hip QOL (Mini-OAKHQOL) scores change from Baseline at Weeks 4 and 12
- Work Productivity and Activity Impairment Questionnaire for Osteoarthritis (WPAI: OA) impairment scores change from Baseline at Weeks 4 and 12.

#### **13.1.4. Safety Endpoints**

- The incidence of treatment-emergent AEs, AEs leading to discontinuation of the study drug, SAEs, and other significant AEs.
- Change from Baseline in clinical laboratory tests, ECG findings, body weight, physical examination findings, and vital signs.
- Dermal assessments: irritation, discomfort, and adhesion.

#### **13.2. Sample Size Determination**

Based on the HP-5000 Phase 2 study results, the assumed [REDACTED] of the test product in the pivotal study will be about [REDACTED]. The sample size of [REDACTED] subjects per treatment arm (or total of about [REDACTED] subjects) will be included in order to have 80% power to demonstrate statistically significant difference versus placebo using a 2-sided overall Type I Error rate of 0.05.

A sufficient number of subjects will be screened to randomize the proposed sample size.

#### **13.3. Analysis Populations**

The following analysis populations are planned for this study:

- Intent-to-Treat (ITT): Includes all consented and randomized subjects. Regardless of any protocol deviations, analyses performed on the ITT set will be based on the randomized treatment assignment and all available data. The ITT will be used as the primary set for analysis of efficacy endpoints.
- Safety Analysis Set (SAF): Includes all subjects who have had at least 1 patch of double-blind study drug applied and who have at least 1 post-dose safety measurement during the Double-blind Treatment Phase. In the unlikely event that errors may have occurred in treatment arm assignments, then analyses using the SAF will be based on treatment actually received. The SAF will be used for the analysis of dermal evaluations and safety endpoints.

Inclusion in the analysis populations will be determined prior to database lock.

If a subject is randomized incorrectly or is administered the incorrect study drug, analyses of the ITT population will be based on the assigned treatment whereas all other analyses will be based on the actual treatment.

## **13.4. Statistical Analyses**

This section presents a summary of the planned statistical analyses. A Statistical Analysis Plan (SAP) that describes the details of the analyses to be conducted will be written prior to database lock. Unless otherwise indicated, all testing of statistical significance will be 2-sided, and a difference resulting in a *P* value of  $<0.05$  will be considered statistically significant. For analyses involving study site, if the number of subjects per site is small, sites may be pooled for analysis, or omitted from statistical models. The final determination will be made prior to database lock.

Summary statistics will be provided for the variables described below. For continuous variables, these statistical analyses will typically include the number of subjects, mean, standard deviation (SD), median, minimum, and maximum. For categorical variables, these statistics will typically include the number and percentage of subjects in each category.

### **13.4.1 Study Subjects and Demographics**

#### **13.4.1.1 Disposition and Withdrawals**

The numbers of subjects randomized, completing, and withdrawing, along with reasons for withdrawal will be tabulated overall and by treatment group. The number of subjects and patches in each analysis population will be reported.

#### **13.4.1.2 Protocol Deviations**

A by-subject listing of all protocol deviations and violations will be reported in the clinical study report (CSR).

#### **13.4.1.3 Demographics and Other Baseline Characteristics**

These analyses will be conducted for all analysis populations. Demographic variables will include age, gender, height, weight, BMI, target knee (left or right), duration of OA of the knee and age at the onset of the disease. Information on race and ethnicity will be collected for any eventual analysis of differences in response to study drug, in accordance with local regulatory requirements. Baseline subject characteristics will include medical history, physical examination findings, and previous OA treatment modalities.

Prior and concomitant medications will be summarized by treatment group, by the number and percentage of subjects taking each medication, classified using World Health Organization Drug Dictionary (WHO-DD) Anatomical Therapeutic Chemical (ATC) classes and preferred terms.

### **13.4.2 Exposure and Compliance**

Investigational product administration will be summarized in terms of the number of patches applied and removed, the number of patches removed earlier along with the summary of reasons for early removal. For each subject mean in terms of duration of exposure will be calculated. Descriptive statistics for these quantities, including the mean, median, SD, minimum, maximum, and quartiles, will be provided by treatment group.

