#### 11.2.2.3 Action Taken

Action taken may consist of:

Drug withdrawn	An indication that a medication schedule was modified through termination of a prescribed regimen of medication.
Dose interrupted	Patch temporarily removed
Dose not changed	No action taken with study drug
Not applicable	Determination of a value is not relevant in the current context.
Unknown	Not known, not observed, not recorded, or refused.

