**At home, subjects are required to conduct the following assessments/procedures:**

1. Remove the patch before showering/bathing and apply a new patch on the target knee (inner or outer by [REDACTED] rotation) approximately every [REDACTED]  
[REDACTED]
2. Perform the following assessments and record in the eDiary on daily basis:
  - a. Record patient eDiary information [REDACTED] when subjects replace the patch and before they sleep.

- b. Perform and record scoring of the pain of the target knee using the NRS 11-point pain scale when subjects replace the patch. The time of NRS assessment will be recorded in the eDiary. In addition to the regular assessment of NRS, the NRS assessment will be performed immediately before the subject takes any rescue medication on the day (if applicable).
- c. Record the time of patch application and removal when subjects replace the patch.
- d. Record the time of unscheduled complete patch detachment and the reason (if applicable) at the time of unscheduled detachment or before they sleep.
- e. Record the number of tablets of rescue medication used, the time and the reason (if applicable) when subjects take a tablet or before they sleep.
- f. Answer the questionnaires related to adhesion, skin irritation and discomfort when subjects replace a patch and record any issues with adhesion, skin irritation and discomfort.

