### **13.4.2 Exposure and Compliance**

Investigational product administration will be summarized in terms of the number of patches applied and removed, the number of patches removed earlier along with the summary of reasons for early removal. For each subject mean in terms of duration of exposure will be calculated. Descriptive statistics for these quantities, including the mean, median, SD, minimum, maximum, and quartiles, will be provided by treatment group.

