14. STUDY MEDICATION EXPOSURE

Exposure to study medication will be presented for the SAF Set. Investigational product administration for each subject will be summarized in terms of the total number of patches applied by visit, number of patches removed early (due to safety reasons: irritation, discomfort, etc.) by visit, and summary of the reason for early removal.

Each subject’s duration of exposure (days) will also be calculated and summarized by treatment arm.

Derivation:

Duration of exposure (days) = latest of (last patch application date and last patch removal date)
- date of 1st patch application + 1

Refer to [Appendix 4](#) for more details.

A by-subject listing of all drug exposure information collected will be presented.

Noven Pharmaceuticals, Inc.

Protocol HP-5000-US-07

Statistical Analysis Plan

Page 26 of 58

The daily amount of rescue medication used and the daily amount of study drug used will be calculated and presented in a by-subject listing. Deviations from the planned doses (overdose, missed dose, or timing) will be recorded on the eCRF and presented in by-subject listing.

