APPENDIX 4. STUDY MEDICATION EXPOSURE DERIVATIONS

The date of 1st patch application will be collected in the Patch Application at site at Visit 3 eCRF page.

The last patch application date will be the latest date collected in the *Scheduled Patch Diary* or *Unscheduled Patch Diary* eCRF pages.

The last patch removal date will be the latest date collected in the *Scheduled Patch Diary*, *Unscheduled Patch Diary*, as well as in the *Patch Removal at the site at final visit* eCRF page.

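### SAP 14 reports exposure as the span from first to last patch, so patch-free days count as exposed, and it counts early removals for safety reasons only, which is narrower than protocol 13.4.2

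*Protocol*

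**What the plan says.** **Protocol 13.4.2 (Exposure and Compliance).** The summary is to cover patches applied, patches removed, and "the number of patches removed earlier along with the summary of reasons for early removal". No reason is excluded. It then says "For each subject mean in terms of duration of exposure will be calculated", and it asks for descriptive statistics that include quartiles, by treatment group. The file contains two versions of the protocol, and these requirements are the same in both.

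**SAP 14 and Appendix 4.** The derivation begins "Duration of exposure (days) = latest of (last patch application date and last patch removal date"; the first application date is then subtracted and 1 added. Appendix 4 only names the source pages, for example "The date of 1st patch application will be collected in the Patch Application at site at Visit 3 eCRF page", and makes no deduction for gaps. For early removals SAP 14 plans the "number of patches removed early (due to safety reasons: irritation, discomfort, etc.) by visit", followed by a summary of reasons. It plans patches applied by visit but not patches removed, and it does not mention quartiles. The default statistics in SAP 8 do not include quartiles either.

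**SAP 3.3** states that changes from the protocol are not applicable.

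**Patch-free time is foreseen.** Protocol 11.2.2.3 defines a dose interruption as "Patch temporarily removed". Protocol 9.2 has a subject whose replacement patch also comes off wait for the next scheduled change.

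**Timing data are collected.** The home procedures in protocol 10.1.3 include "Record the time of patch application and removal when subjects replace the patch", and separately the time and reason of any unscheduled complete detachment.

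**The concern.** A first-to-last span records how long a subject was in the treatment period, not how long the product was on the skin. For a patch the two can differ, because wear can be interrupted or a patch lost without treatment ending. The plan itself treats such time as important: removal or detachment for more than 24 hours before a WOMAC assessment is an intercurrent event in the primary estimand. Yet no planned table shows how much patch-off time each arm had.

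Restricting early removals to safety reasons leaves a second gap. A patch taken off early because it was lifting, or for convenience, would not be in the SAP 14 count, although the protocol asks for it and adhesion is a stated study objective. Someone reading the report to judge tolerability and adherence would see a duration that cannot fall below the calendar span and a count of early removals that is too low by an unknown amount.

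**Working it through.** The documents state no exposure figure to reproduce. The check is a comparison of texts plus an illustration of the formula.

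**Protocol 13.4.2 against SAP 14**

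| Item | Protocol 13.4.2 | SAP 14 |
|---|---|---|
| Patches applied | yes | yes, by visit |
| Patches removed | yes | not named |
| Early removals | all, with reasons | count limited to safety reasons |
| Duration | a per-subject mean, undefined | first-to-last span |
| Quartiles | yes | not named |
| Change declared (SAP 3.3) | – | none |

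**Illustration of the formula.** Assumptions: first patch on Day 0, last removal on Day 84, one patch per day (the interval is redacted), hence 84 scheduled patches, and *g* patch-free days.

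- SAP duration = 84 − 0 + 1 = 85 days, whatever *g* is.
- Days worn = 84 − *g*.
- Overstatement = 85 / (84 − *g*) − 1.
- Compliance under SAP 15, with no replacement patches = (84 − *g*) / 84. The compliant range is 80% to 120%.

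| *g* | SAP duration | Days worn | Overstatement | Compliance |
|---|---|---|---|---|
| 0 | 85 | 84 | 1.2% | 100.0% |
| 7 | 85 | 77 | 10.4% | 91.7% |
| 14 | 85 | 70 | 21.4% | 83.3% |
| 16 | 85 | 68 | 25.0% | 81.0% |
| 17 | 85 | 67 | 26.9% | 79.8% |
| 28 | 85 | 56 | 51.8% | 66.7% |
| 42 | 85 | 42 | 102.4% | 50.0% |

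The 1.2% at *g* = 0 arises only because the formula counts both end dates.

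**Does compliance reveal the gap?** Only in part. Up to 16 patch-free days the subject is still compliant. SAP 15 also takes unscheduled applications into account. If that means they count as used patches, 21 patch-free days with 10 replacements gives (63 + 10) / 84 = 73/84 = 86.9%. That subject is compliant, with 85 days of exposure shown against 63 worn (34.9% too high).

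**Do other outputs supply the missing quantities?** SAP 18.7.1.1 scores adhesion at clinic visits, including a category for a detached patch. SAP 18.7.2 counts at-home adhesion events. SAP 14 lists exposure data by subject. None of these summarizes worn time or gives early removals for all causes by reason.

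**The case against.** The strongest reply is that little depends on this. A reader might infer that overstated exposure dilutes the adverse event and dermal rates. The documents do not support that. SAP 18.1 tabulates numbers and percentages of subjects, SAP 18.7.1 counts subjects or patches, and SAP 18.7.2 counts events. No planned rate uses duration as a denominator. Nor do the documents support a claim that the more irritating arm would be favored: that depends on interruption patterns not yet known, and protocol 5.3 reports good dermal tolerability in Phase 2.

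A reader might also infer that the protocol plainly requires wear time per patch. Its sentence is too unclear for that. A per-subject mean fits wear time per patch naturally, since a single span leaves nothing to average, but protocol 13.4 calls itself a summary and leaves details to the SAP. A span is a legitimate quantity if labeled as one.

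It would also be too strong to say that adhesion losses go unreported, because SAP 18.7.1.1 and 18.7.2 cover them in part. Removal and detachment are recorded separately, so early removal may fairly mean deliberate removal. SAP 14's summary of reasons carries no safety restriction of its own.

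Long gaps may be uncommon. The wait after a second detachment ends at the next scheduled change, and protocol 9.9 requires counseling after two consecutive missed days.

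These replies limit the consequence. They do not remove the safety-only restriction on the count, the missing items, or the statement that nothing changed.

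**Conclusion.** The point holds as a defect in the descriptive exposure summary. Read as written, the SAP gives a duration that cannot show patch-free time, an early-removal count narrower than the protocol's, and no stated plan for patches removed or quartiles, with none of this declared in SAP 3.3. The table shells mentioned in SAP 8 were not available; they could contain quartiles, but the SAP text does not.

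In the illustration the overstatement is 25% for a subject just inside the compliance limit. That figure rests on daily patches and a full Day 0 to Day 84 course, and it is not a forecast. The effect is confined to exposure reporting and to how tolerability and adherence are interpreted. Sample size, power, the primary test and the planned safety percentages are unaffected. The correction is worth making because it is cheap.

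**What to change.** In SAP 14 and Appendix 4:

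1. Keep the current formula but label it *time from first to last patch*.
2. Add total days worn and each subject's mean wear time per patch, from the eDiary application, removal and unscheduled-detachment times, with quartiles by arm.
3. End wear time at a recorded detachment, and exclude off-skin time where it is recorded.
4. Where a removal time is missing, cap wear at the scheduled interval or report the value as missing. Do not set it to the next application time, because that would count the gap as wear again.
5. Drop the safety-only restriction. Tabulate early removals by reason for all reasons, with complete detachments as a separate category, and add the number of patches removed. Confirm that the patch diary forms hold a reason for deliberate early removal; the home procedures name a reason only for detachment.
6. Declare in SAP 3.3 any departure from protocol 13.4.2 that is kept.

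The cost is SAP wording, some programming and a missing-time rule. The application, removal and detachment times are already collected, and no trial procedure changes.
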